10.2.5 Assessment of Intensity

The investigator will make an assessment of intensity for each AE reported during the study. An intensity grade will be assigned to each AE. The intensity grading scales used in this study are adapted from the "FDA Guidance for Industry: Toxicity Grading Scale for Healthy Adult and Adolescent Volunteers Enrolled in Preventive Vaccine Clinical Trials, September 2007".

10.2.5.1 Tables for Clinical Abnormalities

10.2.5.1.1 Solicited AR Intensity Grading Scale

Table 10.1: Solicited injection site reactions: terminology, definitions, and intensity scales – Children aged 2 through 11 years

CRF term (MedDRA lowest level term [LLT])	Injection site pain	Injection site erythema	Injection site swelling	Injection site induration	Injection site bruising
Diary card term	Pain	Redness	Swelling	Hardening	Bruising
Definition	Pain either present spontaneously or when the injection site is touched or injected limb is mobilized	Presence of a redness including the approximate point of needle entry	Swelling at or near the injection site Swelling or edema is caused by a fluid infiltration in tissue or cavity and, depending on the space available for the fluid to disperse, swelling may be either soft (typically) or firm (less typical) to touch and thus can be best described by looking at the size of the swelling	Hardening at or near the injection site. Hardening is caused by a slow diffusion of the product in the tissue leading to a thick or hard area to touch at or near the injection site and thus can be best described by looking at the size of the hardening.	Bruising is the result of the diffusion of blood in the skin from ruptured blood vessels that forms a purple or black and blue spot on the skin. It can be best described by looking at its size.
Intensity scale*	CRF:	Grade 1: > 0 to	Grade 1: > 0 to < 25 mm	Grade 1: > 0 to < 25 mm	Grade 1: > 0 to < 25 mm
	Grade 1: Easily tolerated	< 25 mm	Grade $2: \ge 25$ to < 50 mm	Grade $2: \ge 25$ to < 50 mm	Grade $2: \ge 25$ to < 50 mm
	Grade 2: Sufficiently discomforting to interfere with normal behavior or activities	Grade $2: \ge 25$ to < 50 mm Grade $3: \ge 50$ mm	Grade 3: ≥ 50 mm	Grade 3: ≥ 50 mm	Grade 3: ≥ 50 mm
	Grade 3: Incapacitating, unable to perform usual activities				

Diary card:		
Grade 1: No interference with activity		
Grade 2: Some interference with activity		
Grade 3: Significant; prevents daily activity		

VAP00027

Protocol Version 2.0

MedDRA: Medical Dictionary for Regulatory Activities

^{*} For pain, the scale will be provided in the CRF and the intensity will be transcribed from the diary card. For other injection site reactions (erythema and swelling), the classification as Grades 1, 2, or 3 will be applied at the time of statistical analysis; the scale is provided for information purposes only. The actual size of the reaction will be reported in the CRF.

Table 10.2: Solicited injection site reactions: terminology, definitions, and intensity scales – Adolescents and adults aged≥ 12 years

CRF term (MedDRA lowest	Injection site pain	Injection site erythema	Injection site swelling	Injection site induration	Injection site bruising
level term [LLT])	Da:	·	Constline	Handanin a	Desirie
Diary card term	Pain	Redness	Swelling	Hardening	Bruising
Definition	Pain either present spontaneously or when the injection site is touched or injected limb is mobilized	Presence of a redness including the approximate point of needle entry	Swelling at or near the injection site Swelling or edema is caused by a fluid infiltration in tissue or cavity and, depending on the space available for the fluid to disperse, swelling may be either soft (typically) or firm (less typical) to touch and thus can be best described by looking at the size of the swelling	Hardening at or near the injection site. Hardening is caused by a slow diffusion of the product in the tissue leading to a thick or hard area to touch at or near the injection site and thus can be best described by looking at the size of the hardening.	Bruising is the result of the diffusion of blood in the skin from ruptured blood vessels that forms a purple or black and blue spot on the skin. It can be best described by looking at its size.

Intensity	CRF:	Grade 1:	Grade 1: \geq 25 to \leq 50 mm	Grade 1: > 0 to < 25 mm	Grade 1: > 0 to < 25 mm
scale*	Grade 1: A type of adverse event that is	\geq 25 to	Grade $2: \ge 51$ to ≤ 100 mm	Grade 2: \geq 25 to \leq 50 mm	Grade $2: \ge 25$ to < 50 mm
	usually transient and may require only	≤ 50 mm	Grade 3: > 100 mm	Grade $3: \ge 50 \text{ mm}$	Grade $3: \ge 50 \text{ mm}$
	minimal treatment or therapeutic	Grade 2:			
	intervention. The event does not generally	\geq 51 to			
	interfere with usual activities of daily	$\leq 100 \text{ mm}$			
	living.	Grade 3:			
	Grade 2: A type of adverse event that is	> 100 mm			
	usually alleviated with additional				
	therapeutic intervention. The event				
	interferes with usual activities of daily				
	living, causing discomfort but poses no				
	significant or permanent risk of harm to				
	the research participant.				
	Grade 3: A type of adverse event that				
	interrupts usual activities of daily living, or				
	significantly affects clinical status, or may				
	require intensive therapeutic intervention.				
	Diary card:				
	Grade 1: No interference with activity				
	Grade 2: Some interference with activity				
	Grade 3: Significant; prevents daily				
	activity				

MedDRA: Medical Dictionary for Regulatory Activities

^{*} For pain, the scale will be provided in the CRF and the intensity will be transcribed from the diary card. For other injection site reactions (erythema and swelling), the classification as Grades 1, 2, or 3 will be applied at the time of statistical analysis; the scale is provided for information purposes only. The actual size of the reaction will be reported in the CRF.

Table 10.3: Solicited systemic reactions: terminology, definitions, and intensity scales – Children aged 2 through 11 years, adolescents or adults aged \geq 12 years

CRF term (MedDRA lowest level term [LLT])	Fever	Headache	Malaise	Myalgia	Chills
Diary card term	Temperature	Headache	Feeling unwell	Muscle aches and pains	Chills
Definition	Elevation of temperature to ≥°38.0°C (≥ 100.4°F)	Pain or discomfort in the head or scalp. Does not include migraine.	General ill feeling. Malaise is a generalized feeling of discomfort, illness, or lack of well-being that can be associated with a disease state. It can be accompanied by a sensation of exhaustion or inadequate energy to accomplish usual activities.	Muscle aches and pains are common and can involve more than one muscle at the same time. Muscle pain can also involve the soft tissues that surround muscles. These structures, which are often referred to as connective tissues, include ligaments, tendons, and fascia (thick bands of tendons). Does not apply to muscle pain at the injection site which should be reported as injection site pain.	Cold feeling
Intensity scale*	Grade 1: ≥ 38.0°C to	CRF:	CRF:	CRF:	CRF:
	≤ 38.4 °C, or ≥ 100.4 °F to ≤ 101.1 °F	Grade 1: A type of adverse event that is usually transient and may require only minimal treatment or therapeutic intervention. The event does not generally interfere with usual activities of daily living.	Grade 1: A type of adverse event that is usually transient and may require only minimal treatment or therapeutic intervention. The event does not generally interfere with usual activities of daily living.	Grade 1: A type of adverse event that is usually transient and may require only minimal treatment or therapeutic intervention. The event does not generally interfere with usual activities of daily living.	Grade 1: A type of adverse event that is usually transient and may require only minimal treatment or therapeutic intervention. The event does not generally interfere with usual activities of daily living.

Grade 2: $\geq 38.5^{\circ}$ C to $\leq 38.9^{\circ}$ C, or $\geq 101.2^{\circ}$ F to $\leq 102.0^{\circ}$ F	Grade 2: A type of adverse event that is usually alleviated with additional therapeutic intervention. The event interferes with usual activities of daily living, causing discomfort but poses no significant or permanent risk of harm to the research participant.	Grade 2: A type of adverse event that is usually alleviated with additional therapeutic intervention. The event interferes with usual activities of daily living, causing discomfort but poses no significant or permanent risk of harm to the research participant.	Grade 2: A type of adverse event that is usually alleviated with additional therapeutic intervention. The event interferes with usual activities of daily living, causing discomfort but poses no significant or permanent risk of harm to the research participant.	Grade 2: A type of adverse event that is usually alleviated with additional therapeutic intervention. The event interferes with usual activities of daily living, causing discomfort but poses no significant or permanent risk of harm to the research participant.
Grade $3: \ge 39.0$ °C or ≥ 102.1 °F	Grade 3: A type of adverse event that interrupts usual activities of daily living, or significantly affects clinical status, or may require intensive therapeutic intervention.	Grade 3: A type of adverse event that interrupts usual activities of daily living, or significantly affects clinical status, or may require intensive therapeutic intervention.	Grade 3: A type of adverse event that interrupts usual activities of daily living, or significantly affects clinical status, or may require intensive therapeutic intervention.	Grade 3: A type of adverse event that interrupts usual activities of daily living, or significantly affects clinical status, or may require intensive therapeutic intervention.
	Diary card: Grade 1: No interference			
	with activity	with activity	with activity	with activity
	Grade 2: Some interference with activity			
	Grade 3: Significant; prevents daily activity			

MedDRA: Medical Dictionary for Regulatory Activities

^{*} For all reactions (except fever), the scale will be provided in the CRF and the intensity will be transcribed from the diary card. For fever, the body temperature will be recorded, and the classification as Grade 1, 2, or 3 will be assigned at the time of the statistical analysis based on the unit used to measure the temperature and the intensity scale.

Important notes for the accurate assessment of temperature:

Participants or parents / legally acceptable representatives are to measure body temperature once per day, preferably always at the same time. The optimal time for measurement is the evening, when body temperature is the highest. Temperature is also to be measured at the time of any apparent fever. The observed daily temperature and the route of measurement are to be recorded in the DC / eDC / MA, and the highest temperature will be recorded by the site in the CRF. The preferred route for this study is oral.

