8.3.8 Early Safety Data Review

An ESDR conducted by the Safety Management Team (SMT) will be performed, the goal of
which is to allow for a cautious, stepwise approach to vaccine administration. An initial safety
review for this study is planned when approximately 10% of participants aged 9 to 17 years
are vaccinated and have provided safety data for 7 days after administration of the study
intervention.

- The safety data collected will be entered into the case report book (CRB) and will be summarized and reviewed by the Sponsor. It is understood that this review will be based on preliminary data that would not have been subject to validation and database lock.
- The following safety parameters collected from D01 to D08 will be assessed as part of the ESDR review by the Sponsor:
 - Immediate reactions
 - Solicited injection site and systemic reactions
 - Unsolicited AEs reported as related by the investigator
 - SAEs (including AESIs)
- Enrollment will not be paused during the Sponsor review.
- If any of the following criteria are met, a decision will be made by the Sponsor as to whether enrollment in the study will be paused and will be allowed to resume later:
 - An SAE (including AESI) considered as related to the vaccination by the investigator and Sponsor
 - > 10% of participants experiencing any Grade 3 AEs within 7 days after vaccination
- After the ESDR is conducted, the team will continue to monitor the safety of all participants via SMT and/or data review meetings during the conduct of the study. SMT periodicity will be detailed in the SMT charter.

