4.2.1 Safety

4.2.1.1 Solicited Reactions

4.2.1.1.1 Daily Intensity

All daily records for solicited reactions will be derived into daily intensity according to the following classification: None, Grade 1, Grade 2, Grade 3, or Missing (Unknown).

For the derivation of daily intensities, the following sequential steps will be applied:

- 1) Solicited reactions (except Fever/Pyrexia) with CRF presence recorded as "No" and with all daily records missing (Unknown) then all daily intensities will be derived as None.
- 2) For non-measurable solicited reactions, daily intensities will correspond to daily records reported in the clinical database. For measurable solicited reactions the daily measurements reported in the clinical database will be converted based upon the intensity scales defined in the protocol; this assumes a reaction that is too large to measure (non-measurable, "NM") is Grade 3. Note: the intensity could be considered "None" (not a reaction) in the analysis despite being considered a reaction by the investigator (e.g., swelling measurement > 0 mm but < 25 mm in adults).

Note: The maximum intensity on the ongoing period is derived from the record of the maximum intensity/measurement after the end of the solicited period following the rule described above.

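### In Table 10.2 (age 12 and over), induration and bruising are graded on the 2–11-year cut-offs but erythema and swelling are not, with no reason given, so equal sizes up to 100 mm receive a different presence or grade

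*Protocol*

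**What the plan says.** Protocol Section 10.2.5.1.1 has one table of injection-site scales for ages 2–11 (Table 10.1) and one for age 12 and over (Table 10.2). In Table 10.1 all four measurable reactions share one scale, with Grade 1 at "Grade 1: > 0 to < 25 mm" and Grade 3 from 50 mm.

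In Table 10.2 the swelling column begins at "Grade 1: \geq 25 to \leq 50 mm" and ends at "Grade 3: > 100 mm", and erythema has the same cut-offs. The induration and bruising columns of the same table begin at "Grade 1: > 0 to < 25 mm" and reach Grade 3 from 50 mm. As the text reads, Grade 2 induration is "Grade 2: \geq 25 to \leq 50 mm", whereas the bruising column and Table 10.1 stop below 50 mm.

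The Table 10.2 footnote says: "For other injection site reactions (erythema and swelling), the classification as Grades 1, 2, or 3 will be applied at the time of statistical analysis". It does not mention induration or bruising. It also says that the measured size is entered in the CRF.

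SAP 4.2.1.1.1 converts daily measurements of measurable solicited reactions to grades using the protocol scales. It warns that a measured reaction may be analysed as absent, and its only example is "swelling measurement > 0 mm but < 25 mm in adults". Under SAP 4.2.1.1.2 to 4.2.1.1.5 and 4.2.1.1.7, maximum intensity, presence, onset, days of occurrence and ongoing status all follow from the daily grade.

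**The concern.** Within one age group, the threshold for being counted at all, and the threshold for Grade 3, depend on which term is recorded and not only on the size measured. The terms are not fully separate: the swelling definition allows that "swelling may be either soft (typically) or firm (less typical) to touch", and induration is defined as a hard or thick area at or near the injection site. A firm raised area could reasonably be entered under either term.

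Solicited reactions are a key secondary endpoint. The documents supplied contain no table shells, so the point is conditional: if an any-reaction or Grade 3 injection-site total is produced for age 12 and over, it adds events defined in two different ways. A reader who compares the four reactions with each other in this age group would also be comparing thresholds.

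**Working it through.** The plan states no figure on this point, so there is none to reproduce. The check applies the cut-offs as read.

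**Inputs.** Table 10.2 erythema and swelling: Grade 1 is 25–50 mm, Grade 2 is 51–100 mm, Grade 3 is above 100 mm. Table 10.2 bruising: Grade 1 is above 0 and below 25 mm, Grade 2 is 25 to below 50 mm, Grade 3 is 50 mm or more. Table 10.2 induration: as bruising, but with Grade 2 running up to and including 50 mm as read. Table 10.1, all four reactions: identical to the bruising scale.

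**Step 1: grade each whole millimetre from 1 to 200 at age 12 and over.**

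| Size (mm) | Erythema, swelling | Induration | Bruising |
|---|---|---|---|
| 1–24 | None (absent) | Grade 1 | Grade 1 |
| 25–49 | Grade 1 | Grade 2 | Grade 2 |
| 50 | Grade 1 | Grade 2 and Grade 3, as read | Grade 3 |
| 51–100 | Grade 2 | Grade 3 | Grade 3 |
| 101–200 | Grade 3 | Grade 3 | Grade 3 |

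The two pairs of columns disagree at all 100 whole-millimetre sizes from 1 to 100 and agree only above 100 mm.

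**Step 2: compare with Table 10.1.** The Table 10.2 bruising column matches the 2–11-year scale at every size. The induration column differs from it only at exactly 50 mm.

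**Step 3: direction for Grade 3.** Every induration or bruise above 100 mm is Grade 3 on both scales. Those of 50–100 mm are Grade 3 on the printed scale and would be at most Grade 2 on the erythema and swelling scale. The Grade 3 rate for these two terms is therefore equal or higher on the printed scale. The difference is the share of participants whose largest such lesion is 50–100 mm (at exactly 50 mm for induration, subject to the boundary question). The documents give no size distribution, so this share is unknown.

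**Step 4: how many participants the table covers.** The plan has 667 adults and 667 participants aged 9–17, of whom at least 30% are to be 9–11 years old (Protocol synopsis). At most 0.70 × 667 ≈ 467 are therefore aged 12–17. The upper limit is 667 + 467 = 1134, and 1134/1334 = 85%. This is the population graded on Table 10.2, not the number whose grade would change.

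**The case against.** Different reaction terms may properly have different scales. Protocol Section 10.2.5 says the scales are adapted from an external guidance, so a deliberate choice cannot be excluded. Apart from 50 mm for induration, each column is unambiguous and can be programmed, and the SAP's swelling example agrees with Table 10.2. Keeping one scale for induration and bruising also makes them comparable across age 12, inside the 9–17 group; erythema and swelling lose that comparability. All of this stands. It means the documents do not establish an error in either pair of columns, only an unexplained difference.

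A reader might infer that Grade 3 rates are inflated, or that 50–100 mm induration and bruising drive the Grade 3 count. The first assumes that the erythema and swelling scale is the right one for the other two terms, which nothing in the documents says. The second needs a size distribution that is not given, and pain adds Grade 3 events on a scale unrelated to size. A reader might also infer that one lesion is graded twice, or that 85% of participants are affected. These are separate CRF terms, and overlap in definition is shown only for firm swelling and induration, not for bruising.

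The footnote is weak evidence of an oversight, because the same wording stands under Table 10.1, where all four scales agree. The 50 mm overlap rests on one comparison sign and may come from the PDF reading.

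The early safety data review criterion ("> 10% of participants experiencing any Grade 3 AEs within 7 days after vaccination", Protocol 8.3.8) could draw on these grades for ages 12–17. But it leads to a sponsor decision, it has its own SAP (SAP 3.6), which is not supplied, and it was set at about 10% of the 9–17 group. SAP Section 5 records enrolment as complete, so a change in grading now would not alter that review.

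**Conclusion.** The point holds as one of unexplained and unreconciled definitions. At age 12 and over, reactions of equal size from 1 to 100 mm receive a different presence or grade depending on the term recorded, and pooled injection-site totals at that age would combine two definitions. Grade 3 rates for induration and bruising are the same as or higher than on the other scale, by an amount that cannot be calculated from the documents. Of up to about 1134 participants graded on Table 10.2, only those with induration or bruising of 100 mm or less could be graded differently if the erythema and swelling scale applied to those terms.

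This rests on the cut-offs as extracted, on sizes in whole millimetres, and on literal use of SAP 4.2.1.1.1. It takes no position on which scale is intended. The effect is confined to descriptive safety results; the non-inferiority tests, sample size and alpha are untouched.

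**What to change.** 1. Reconcile the Table 10.2 columns, the footnote (so that it covers all four measurable reactions) and SAP 4.2.1.1.1. Alternatively, state in both documents that two scales are intended at age 12 and over, and why.
2. Check the 50 mm boundary for induration against the original table, so that no size falls in two grades.
3. Either way, keep all four reactions in the pooled totals. Leaving induration and bruising out would remove genuine solicited reactions from the main safety summary.
4. Add one table of the largest recorded size per participant for erythema, swelling, induration and bruising, in common bands: above 0 to below 25, 25 to below 50, exactly 50, above 50 to 100, and above 100 mm. These bands add up to the grades of either scale, and the separate 50 mm band covers the boundary question. Show reactions too large to measure on their own line, since SAP 4.2.1.1.1 makes them Grade 3 in every case.

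The cost is a clarification and one extra table. Sizes are already in the CRF and grades are assigned at analysis, so data collection does not change. If the induration and bruising cut-offs are changed, their graded rates may no longer match earlier studies that used the same table, or the scale used at 9–11 years.

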10.2.5.1.2 Unsolicited AE Intensity Grading Scale

For measurable unsolicited AEs that are part of the list of solicited reactions, the corresponding scale for solicited reactions will be used (see Section 10.2.5.1.1).

All other unsolicited AEs will be classified according to the following intensity scale:

- Grade 1
 - CRF: A type of adverse event that is usually transient and may require only minimal treatment or therapeutic intervention. The event does not generally interfere with usual activities of daily living.
 - DC: No interference with activity.
- Grade 2
 - CRF: A type of adverse event that is usually alleviated with additional therapeutic intervention. The event interferes with usual activities of daily living, causing discomfort but poses no significant or permanent risk of harm to the research participant.
 - DC: Some interference with activity.
- Grade 3
 - CRF: A type of adverse event that interrupts usual activities of daily living, or significantly affects clinical status, or may require intensive therapeutic intervention.
 - DC: Significant; prevents daily activity.

10.3 Appendix: Contraceptive and Barrier Guidance

10.3.1 Definitions

Woman of Childbearing Potential (WOCBP)

A woman is considered fertile following menarche and until becoming postmenopausal unless permanently sterile (see below).

If fertility is unclear (eg, amenorrhea in adolescents or athletes) and a menstrual cycle cannot be confirmed before first dose of study intervention, additional evaluation should be considered.

Women in the following categories are not considered WOCBP

- 1) Premenarchal
- 2) Premenopausal female with 1 of the following:
 - Documented hysterectomy
 - Documented bilateral salpingectomy
 - Documented bilateral oophorectomy

For individuals with permanent infertility due to an alternate medical cause other than the above, (eg, mullerian agenesis, androgen insensitivity), investigator discretion should be applied to determining study entry.

Note: Documentation can come from the site personnel's: review of the participant's medical records, medical examination, or medical history interview.

- 3) Postmenopausal female
 - A postmenopausal state is defined as no menses for 12 months without an alternative medical cause.
 - A high follicle stimulating hormone (FSH) level in the postmenopausal range may be used to confirm a postmenopausal state in women not using hormonal contraception or hormonal replacement therapy (HRT). However, in the absence of 12 months of amenorrhea, confirmation with more than one FSH measurement is required.
 - Females on HRT and whose menopausal status is in doubt will be required to use one of the non-estrogen hormonal highly effective contraception methods if they wish to continue their HRT during the study. Otherwise, they must discontinue HRT to allow confirmation of postmenopausal status before study enrollment.

